I'm here to learn from you during this interview. There are no right or wrong answers and everything you say in this interview will be kept confidential. Our discussion will last about an hour and your participation in this interview is completely voluntary. If at any time you need to stop the interview, just let me know. As a busy clinician, we know that things may come up, so if we do need to end the interview early, but you wish to reschedule to complete the interview in the next 2 weeks, let me know that as well.

Before we get started, I just need to verify that you received our reminder email yesterday and that you have a copy of the materials needed for the interview today. You should have 4 attachments. We will use three of them in the interview: the definitions file, the Scale A file, and the Scale B file. Do you have these materials or should I send you a new copy now? [Send files if needed.]

[If previously agreed to audio recording]

Lastly, as we discussed earlier, I will be audio recording our conversation. I just want to check in and confirm that audio recording the interview is still fine with you.

Yes

Great. I'll start the recorder now.

No

Okay. Instead of audio recording, I'll take detailed notes. I will be writing a lot and may need to pause between questions, but I want you to know that I am listening to you even when I am writing. Let's get started.

[If previously refused audio recording]

Lastly, as we discussed earlier, I will not be audio recording our conversation. However, I will be taking detailed notes of our conversation. I will be writing a lot and may need to pause between questions, but I want you to know that I am listening to you even when I am writing. Let's Get Started.

1

Version Date: 2019_03_21

Interviewer Name: _____

CONFIDENTIAL

**This document is confidential and the property of the Duke University.
Version 1.0 Date: 28 March 2019**

Protocol No.: Pro00102030 Protocol Name: Pediatric Sedation Study Date: _____

Participant ID: _____

Randomization Group: PSSS 1st UMSS 1st

Interview Start Time: _____

Questions:

Sedation Level Definitions

To start, let's pull up the Definitions document that I sent you with your interview reminder email yesterday. I'll give you a few moments to review them and then we will discuss them.

1. Let's start with the definition for sedation. What are your general thoughts about the provided definition for sedation level?
 - a. Do you agree or disagree with definition?
 - b. Would you add or remove anything?
 - c. Applicable from birth to 18 years?
2. Now let's move to Sedation Level Definitions in this document. What are your general impressions of these levels for sedation with regard to how well they define progressive sedation levels? [concept levels]
 - a. If there things about these definitions you would change, what would you change?
 - b. Applicable from birth to 18 years?

Prior Use

3. Which scales have you previously used to measure sedation levels in your pediatric patients?
 - a. **[For any scale mentioned]**
 - i. How long have you used the [name of referenced scale]?
 - ii. What strengths do you think the [name of referenced scale] has?
 - iii. What limitations do you think the [name of referenced scale] has?

CONFIDENTIAL

**This document is confidential and the property of the Duke University.
Version 1.0 Date: 28 March 2019**

Protocol No.: Pro00102030 Protocol Name: Pediatric Sedation Study Date: _____

Participant ID: _____

Randomization Group: PSSS 1st UMSS 1st**Scale Specific Questions – UMSS**

Great! Now let's move on to the specific scales we are considering in this study. I am going to have you pull up the [first scale for randomization group] now. After you've had a couple of minutes to read through it, we'll go through some questions regarding that scale.

4. UMSS: How clear are the scale instructions?
 - i. How helpful are the instructions?
5. Looking at the sedation level categories in this scale, how clearly do you think each level is defined?
 - b. How distinct do you think each category's definition is from the others?
 - c. Are there any terms or phrases that are unclear or might create confusion when scoring a child on these levels?
 - d. What information / patient interaction do you need to assess each level of sedation on this scale.
 - i. What actions would you take to obtain this information?
 1. Awake/Alert vs. tired/sleepy vs. somnolent/sleeping vs. deep sleep
 2. Appropriate response to verbal conversation or sound
 3. Easily aroused with light tactile stimulation or a simple verbal command
 4. Arousal only with significant physical stimulation.
 5. Unarousable
 - e. Are they appropriate for pediatric patients in the following age ranges?
 - i. <2 year
 - ii. 2-6
 - iii. 6-12
 - iv. 12-18
 1. Are each of these levels easily distinguishable based on your clinical experience observing patients?
 - f. How would your clinical decisions or actions change at each of the sedation levels on this scale? **[ensure they speak about all levels]**

3

Version Date: 2019_03_21

Interviewer Name: _____

CONFIDENTIAL

**This document is confidential and the property of the Duke University.
Version 1.0 Date: 28 March 2019**

Protocol No.: Pro00102030 Protocol Name: Pediatric Sedation Study Date: _____

Participant ID: _____ Randomization Group: PSSS 1st UMSS 1st

g. Have you observed patients who fit some criteria for one sedation level on this scale and some criteria for another sedation level?

- i. Which sedation level would you assign the child in this scenario / when they fit into multiple levels?
- ii. What factors do you consider when making this decision?
- iii. How can the scale be modified to minimize this problem? [To level description or instructions]

1. Would you add any instructions to the scale?

Scale Specific Questions – PSSS

Great! Now let's move on to our specific scales we are considering in this study. I am going to have you pull up the [first scale for randomization group] now. After you've had a couple of minutes to read through it, we'll go through some questions regarding that scale.

6. There are no instructions for this scale. How do you think the scale should be completed?
7. Looking at the sedation level categories in this scale, how clearly do you think each level is defined?
 - b. How distinct do you think each category's definition is from the others?
 - c. Are there any terms or phrases that are unclear or might create confusion when scoring a child on these levels?
 - d. What information / patient interaction do you need to assess each level of sedation on this scale.
 - i. What actions would you take to obtain this information?
 1. Not moving vs. Moving vs. movement that requires immobilization
 - a. gentle vs forceful
 2. Discomfort
 - a. Facial expression / frowning
 - b. Verbalization/crying vs. no verbalization or crying
 3. Quiet / Asleep / Deeply asleep

4

Version Date: 2019_03_21

Interviewer Name: _____

CONFIDENTIAL

**This document is confidential and the property of the Duke University.
Version 1.0 Date: 28 March 2019**

Protocol No.: Pro00102030 Protocol Name: Pediatric Sedation Study Date: _____

Participant ID: _____

Randomization Group: PSSS 1st UMSS 1st

4. Vital signs and physiological parameters (oxygen saturation, blood pressure, bradycardia)
 - a. Normal vs. Not Normal
5. Requires airway intervention
- e. Are they appropriate for pediatric patients in the following age ranges?
 - i. <2 year
 - ii. 2-6
 - iii. 6-12
 - iv. 12-18
8. Are each of these levels easily distinguishable based on your clinical experience observing patients?
 - f. How would your clinical decisions or actions change at each of the sedation levels on this scale? [ensure they speak about all levels]
 - g. Have you observed patients who fit some criteria for one sedation level on this scale and some criteria for another sedation level?
 - i. Which sedation level would you assign the child in this scenario / when they fit into multiple levels?
 - ii. What factors do you consider when making this decision?
 - iii. How can the scale be modified to minimize this problem? [To level description or instructions]
 1. Would you add any instructions to the scale?

CONFIDENTIAL

**This document is confidential and the property of the Duke University.
Version 1.0 Date: 28 March 2019**

Protocol No.: Pro00102030 Protocol Name: Pediatric Sedation Study Date: _____

Participant ID: _____

Randomization Group: PSSS 1st UMSS 1st**Head to head comparison of PSSS and UMSS**

Now I would like us to consider both the PSSS and the UMSS scales. I'm going to ask you some questions regarding their similarities and differences as well as your preferences.

9. What strengths do you think each of the scales has?
 - a. [Probe on both scales.]
10. What limitations do you think each of the scales has?
 - b. [Probe on both scales.]
 - c. Does one scale have more ambiguity that might lead to difficulty scoring a child's sedation level?
11. Which of these scales do you think aligns better with the Sedation Level Definitions from the definitions file that we discussed earlier?
12. The PSSS has more categories than the UMSS.
 - d. What do you see as the major differences between the ways these categories are differentiated in each of the scales?
 - i. How important is it to measure levels of sedation with regard to patient safety?
 - e. The PSSS has more categories for deeper sedation levels to assess not only efficacy of the sedation treatment but also safety with regard to sedation level. The UMSS only includes sedation levels with regard to efficacy. How important is it to measure levels of sedation with regard to patient safety?
13. Which of the two scales do you prefer?
 - f. What is it about this scale that you like more than the other?
 - g. Is this preference true for each of the following age groups?
 - i. <2 year
 - ii. 2-6
 - iii. 6-12
 - iv. 12-18

CONFIDENTIAL

**This document is confidential and the property of the Duke University.
Version 1.0 Date: 28 March 2019**

Protocol No.: Pro00102030 Protocol Name: Pediatric Sedation Study Date: _____

Participant ID: _____

Randomization Group: PSSS 1st UMSS 1st**Mapping**

For our last topic, I want to talk with you about how well the sedation categories on each of these scales coincides with our defined sedation levels and with each other.

14. Let's go through each level on the PSSS and map them to the Sedation Level Definitions we discussed earlier. You will need the Scale A and Definitions File for this activity. The PSSS is reverse scored as compared to the UMSS, so make sure you are referring to the correct scale as we talk through the levels. For level 1 on the PSSS, which level definition does that coincide with? **[Continue through each level on the scale.]**

Minimal sedation	5
Moderate Sedation/Analgesia	4
Deep Sedation/Analgesia	3
General anesthesia	2
	1
	0

15. Let's go through each level on the UMSS and map them to the sedation level definitions we discussed earlier. You will need the Scale B and Definitions File for this activity. Remember to check the scale and make sure you are looking at the UMSS as we begin. For level 1 on the UMSS, which level definition does that coincide with? **[Continue through each level on the scale.]**

Minimal sedation	0
Moderate Sedation/Analgesia	1
Deep Sedation/Analgesia	2
General anesthesia	3
	4

CONFIDENTIAL

**This document is confidential and the property of the Duke University.
Version 1.0 Date: 28 March 2019**

Protocol No.: Pro00102030 Protocol Name: Pediatric Sedation Study Date: _____

Participant ID: _____

Randomization Group: PSSS 1st UMSS 1st

16. Now, we're going to do the same sort of mapping between the PSSS and the UMSS. Let's pull up the Scale A and Scale B files and talk through how each sedation level on the PSSS maps to a sedation level on the UMSS. Remember that these are reverse scored compared to one another as we work through this activity.

PSSS	UMSS
5 (Awake)	0 (Awake)
4	1
3	2
2	3
1	4
0	

17. That concludes the questions that we have for you today. Is there anything else you would like to tell us about the PSSS, the UMSS, or other sedation scales that you think is important?

Thank you so much for your time.

Interview End Time: _____

CONFIDENTIAL

**This document is confidential and the property of the Duke University.
Version 1.0 Date: 28 March 2019**

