- 1) Minimal sedation (anxiolysis) is a drug-induced state during which patients respond normally to verbal commands. Although cognitive function and coordination may be impaired, ventilatory and cardiovascular functions are unaffected.
- 2) Moderate Sedation/Analgesia (conscious sedation) is a drug-induced depression of consciousness during which patients respond purposefully¹ to verbal commands, either alone or accompanied by light tactile stimulation. No interventions are required to maintain a patent airway, and spontaneous ventilation is adequate. Cardiovascular function is usually maintained.
- 3) Deep Sedation/Analgesia is a drug-induced depression of consciousness during which patients cannot be easily aroused but respond purposefully¹ following repeated or painful stimulation. The ability to independently maintain ventilatory function may be impaired. Patients may require assistance in maintaining a patent airway, and spontaneous ventilation may be inadequate. Cardiovascular function is usually maintained.
- 4) General anesthesia is a drug-induced loss of consciousness during which patients are not arousable, even by painful stimulation. The ability to independently maintain ventilatory function is often impaired. Patients often require assistance in maintaining a patent airway, and positive-pressure ventilation may be required because of depressed spontaneous ventilation or drug-induced depression of neuromuscular function. Cardiovascular function may be impaired.

Version Date: 2019_03_21

CONFIDENTIAL

**This document is confidential and the property of the Duke University.
Version 1.0 Date: 28 March 2019**

19 Appendix F – Scale A

Pediatric Sedation State Scale (PSSS)

RATER	Definition?
0	Deeply asleep with ABNORMAL physiological parameters (oxygen desaturation/hypotension/tachy or bradycardia (more than 30% off from baseline))
1	Deeply asleep with normal vital signs – REQUIRES some airway intervention to maintain breathing (chin lift, nasal/oral airway, mask vent, etc.) Physiological parameter are NORMAL
2	Patient is quiet (awake or asleep) and not moving, no frown, no verbalization, no crying
3	Patient has an expression of discomfort on the faces or is crying/verbalizing discomfort but NOT moving or impeding the completion of the procedure. May require positioning, but NO restraining to stop movement. May be awake or asleep

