 - a. [Probe on both scales.]
10. What limitations do you think each of the scales has?
 - b. [Probe on both scales.]
 - c. Does one scale have more ambiguity that might lead to difficulty scoring a child's sedation level?
11. Which of these scales do you think aligns better with the Sedation Level Definitions from the definitions file that we discussed earlier?
12. The PSSS has more categories than the UMSS.
 - d. What do you see as the major differences between the ways these categories are differentiated in each of the scales?
 - i. How important is it to measure levels of sedation with regard to patient safety?
 - e. The PSSS has more categories for deeper sedation levels to assess not only efficacy of the sedation treatment but also safety with regard to sedation level. The UMSS only includes sedation levels with regard to efficacy. How important is it to measure levels of sedation with regard to patient safety?
13. Which of the two scales do you prefer?
 - f. What is it about this scale that you like more than the other?
 - g. Is this preference true for each of the following age groups?
 - i. <2 year
 - ii. 2-6
 - iii. 6-12
 - iv. 12-18

CONFIDENTIAL

**This document is confidential and the property of the Duke University.
Version 1.0 Date: 28 March 2019**

Protocol No.: Pro00102030 Protocol Name: Pediatric Sedation Study Date: _____

Participant ID: _____

Randomization Group: PSSS 1st UMSS 1st**Mapping**

For our last topic, I want to talk with you about how well the sedation categories on each of these scales coincides with our defined sedation levels and with each other.

14. Let's go through each level on the PSSS and map them to the Sedation Level Definitions we discussed earlier. You will need the Scale A and Definitions File for this activity. The PSSS is reverse scored as compared to the UMSS, so make sure you are referring to the correct scale as we talk through the levels. For level 1 on the PSSS, which level definition does that coincide with? **[Continue through each level on the scale.]**

Minimal sedation	5
Moderate Sedation/Analgesia	4
Deep Sedation/Analgesia	3
General anesthesia	2
	1
	0

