15. Let's go through each level on the UMSS and map them to the sedation level definitions we discussed earlier. You will need the Scale B and Definitions File for this activity. Remember to check the scale and make sure you are looking at the UMSS as we begin. For level 1 on the UMSS, which level definition does that coincide with? **[Continue through each level on the scale.]**

Minimal sedation	0
Moderate Sedation/Analgesia	1
Deep Sedation/Analgesia	2
General anesthesia	3
	4

CONFIDENTIAL

**This document is confidential and the property of the Duke University.
Version 1.0 Date: 28 March 2019**

Protocol No.: Pro00102030 Protocol Name: Pediatric Sedation Study Date: _____

Participant ID: _____

Randomization Group: PSSS 1st UMSS 1st

16. Now, we're going to do the same sort of mapping between the PSSS and the UMSS. Let's pull up the Scale A and Scale B files and talk through how each sedation level on the PSSS maps to a sedation level on the UMSS. Remember that these are reverse scored compared to one another as we work through this activity.

PSSS	UMSS
5 (Awake)	0 (Awake)
4	1
3	2
2	3
1	4
0	

17. That concludes the questions that we have for you today. Is there anything else you would like to tell us about the PSSS, the UMSS, or other sedation scales that you think is important?

Thank you so much for your time.

Interview End Time: _____

CONFIDENTIAL

**This document is confidential and the property of the Duke University.
Version 1.0 Date: 28 March 2019**

23 Appendix I– Interview Guide – UMSS First

Protocol No.: Pro00102030Protocol Name: Pediatric Sedation Study

Date: _____

Participant ID: _____

Randomization Group: PSSS 1st UMSS 1st

Clinical Outcomes Assessments of Pediatric Sedation

Cognitive Interview Guide

Introduction

Thank you for taking the time to talk with me today. As we talk, I'm going to ask you questions about two Clinician Reported Outcome scales used to assess sedation level in pediatric populations from birth up to 18 years of age. The questions we ask during this interview will help us to assess the clarity / comprehension of response options for each scale and evaluate the ability of the scale to validly capture different sedation levels. We are particularly interested in how the scales perform for assessing sedation levels related to diagnostic and therapeutic procedures.

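### In both interview guides, Q12e describes the PSSS more favourably than the UMSS immediately before Q13 asks which scale the clinician prefers

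*Combined protocol and SAP*

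**What the plan says.** The point lies in Appendix I, in both the PSSS-first guide (section 22) and the UMSS-first guide (section 23), under the head-to-head comparison. Q9 to Q17 are worded alike in the two guides.

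- Q12 opens by remarking that the PSSS has the larger number of levels. Q12d then asks openly how the two scales differ in separating their levels, and Q12d.i asks "How important is it to measure levels of sedation with regard to patient safety".
- Q12e has the interviewer state "The PSSS has more categories for deeper sedation levels to assess not only efficacy of the sedation treatment but also safety", then "The UMSS only includes sedation levels with regard to efficacy", and then repeat the Q12d.i question word for word.
- Q13 follows at once: "Which of the two scales do you prefer". Q13f asks "What is it about this scale that you like more than the other", and Q13g asks whether the preference holds in each of four age bands.
- Q14 to Q16, the mapping exercise, come after Q13.

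Section 3.2 names two co-primary endpoints: comprehension of items and response options, and the physicians' view of how relevant the scale is for capturing sedation levels. Preference is not among them.

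**The concern.** A preference question should be asked before the interviewer characterises the options, or after a balanced account of both. Here the account runs one way: one scale is credited with an extra property, the other is said to lack it, and the respondent is then asked how much that property matters. No advantage of the UMSS and no drawback of the PSSS is stated. A clinician who has just said that safety matters has been given a reason to name the PSSS.

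At stake is the answer to Q13 and its age-group probes. Section 1.1 says that the findings will inform use of the measure in the network's studies. A preference for the PSSS quoted in the summary report could partly reflect the script, and the data would offer no way to separate the two.

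**Working it through.** No formula applies, because the study is qualitative and the point concerns wording and order. The check is a comparison of texts.

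1. **Exposure.** The Q12e wording is in 2 of 2 guides, and Q13 follows it directly in both. Section 6.1 plans 18 to 24 interviews. If interviewers follow the guide, everyone who reaches Q13 has heard Q12e and the unexposed group is 0. Scale order differs between the guides and Q12e does not, so order cannot offset it or reveal its effect.

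2. **Is the safety contrast accurate?** In Appendix F, PSSS level 0 is defined by abnormal physiological parameters and level 1 by the need for airway support. In Appendix G, UMSS levels 0 to 4 are defined by alertness and arousability, and none refers to vital signs or the airway. The contrast is supported.

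3. **Is the opening remark of Q12 accurate?** PSSS levels 0 to 5 make 6; UMSS levels 0 to 4 make 5. Yes.

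4. **What has been collected before Q12e?** Q1 to Q3 cover the definitions and prior use. Q4 to Q8 cover clarity, distinctness and age-appropriateness of each scale. Q9 to Q11 cover strengths, limitations, ambiguity and alignment with the definitions. Q12d asks openly about differences. None of this follows the statement.

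5. **What follows it?** Q13 immediately, and Q14 to Q16 only after Q13 and its probes.

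6. **Would the planned checks prevent it?** The transcript check in section 8.1 looks for interviewers departing from the interview scope, and reading Q12e as written would pass. The weekly review of how well the guides work could notice it, but only after some interviews are done.

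**The case against.** The strongest reply is that little depends on Q13. Section 2 does not make preference an objective, section 3.2 does not make it an endpoint, and section 6.2 plans neither a tally of preferences nor a rule for choosing a scale. Asking openly at Q12d and giving a prompted contrast afterwards is a defensible sequence. The PSSS questions have already taken respondents through vital signs and airway support, and the UMSS probes contain neither, so the contrast is largely in view before Q12e. Respondents hold both scales and can disagree, and Q13f would let coders see an answer that merely echoes the script. All of this stands, and it keeps the point small. It does not supply a reason for making the one-sided statement directly before Q13.

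Three stronger readings are tempting, and the documents do not support them.

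- *That Q12e misstates the number of deep levels.* By label there are two on each scale (PSSS 0 and 1; UMSS 3 and 4). But Q12e speaks comparatively of deeper levels, and Appendix E lists general anesthesia among its sedation levels. Depending on what is treated as deep, the count runs from 0 vs 1 (PSSS 0 and 1 and UMSS 4 all set aside as general anesthesia) to 3 vs 1 (PSSS 2 counted as deep, only UMSS 4 set aside), a difference of -1 to +2. The sentence can also be read as deeper levels that assess safety, which gives 2 (PSSS 0 and 1) against 0. The counts do not show that it is false, and they say nothing about steering.
- *That it gives away the mapping.* Q12e names no level and no definition. The mapping is done level by level with the documents open: "For level 1 on the PSSS, which level definition does that coincide with" at Q14, and at Q16 respondents "talk through how each sedation level on the PSSS maps to a sedation level on the UMSS". Q13 stands in between. Carry-over is possible but speculative.
- *That the label on the Q16 form cues respondents.* The form marks PSSS 5 as awake. Interviews are by telephone, section 5 lists only the definitions and the two scales for use in the interview, and no script has the label read out.

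**Conclusion.** The point holds as a leading-wording risk confined to Q13, overall and in the four age bands, with the likely direction toward the PSSS. The size of any tilt cannot be computed, because no participant who reaches Q13 is planned to be unexposed and the documents give no figure from which to estimate it. Comprehension evidence, and the comparative evidence from Q9 to Q11 and Q12d, is collected before the statement and is not affected.

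A reader might infer that a co-primary endpoint is biased. The documents do not support that: preference is not an endpoint, and the link through the mapping to the relevance endpoint is an inference that no section makes. The conclusion assumes that interviewers read Q12e as written and in the printed order. It is a modest point, worth correcting because the correction is so cheap.

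**What to change.** In both guides:

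1. Delete the two declarative sentences in Q12e and keep the safety question once, in its existing wording. Q12d.i already asks it, so the duplicate goes.
2. Ask Q13, with its probes, before Q12.

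An alternative is to leave the order alone and move the two sentences, with the question attached to them, to after Q16. Q12d.i would then still stand just before Q13, but without the contrast.

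Neither option removes every cue. The PSSS probes on vital signs and airway support would still come before Q13, and under the first option Q12's opening remark and safety question would come just before Q14. Both are neutral compared with the present statement.

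The cost is a small amendment to two guides for IRB submission and the loss of the prompted contrast before the preference question. It needs no extra sample, staff or interview time.

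A separate editorial correction can go in the same amendment: the Q16 interviewer form labels PSSS 5 as awake, while Appendix F allows a sedated or an awake child at that level. The form should match the scale.

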4	Patient is moving during the procedure and requires gentle immobilization or positioning. May appear uncomfortable, verbalize discomfort, or may be crying but this is not a requirement.
5	Patient is moving (purposefully or non-purposefully) in a manner that impedes the proceduralist and requires forceful immobilization. Patient may be sedated or awake. Patient may be crying or shouting (not required however).

Version Date: 2019_03_21

20 Appendix G – Scale B

University of Michigan Sedation Scale (UMSS)

Prior to scoring, assess the child's response to voice, light stimulation, such as stroking the face, and deeper physical stimulation, such as massaging the upper back or tickling the chest or axilla.

0	Awake and alert
1	Minimally sedated: tired/sleepy, appropriate response to verbal conversation and/or sound
2	Moderately sedated: somnolent/sleeping, easily aroused with light tactile stimulation or a simple verbal command
3	Deeply sedated: deep sleep, arousable only with significant physical stimulation
4	Unarousable

Version Date: 2019_03_21

CONFIDENTIAL

**This document is confidential and the property of the Duke University.
Version 1.0 Date: 28 March 2019**

21 Appendix H – Demographics

Pediatric Anesthesia Study

Protocol Number: _____

Patient Study ID: _____

Date: _____

(MM/DD/YYYY)

SOCIODEMOGRAPHIC FORM – CLINICIAN

Please answer the following questions. Complete the blanks or check the boxes next to the category that best describes your situation.

1. What is your age? _____

2. What is your gender: 1 Male 2 Female
3 Self-identify: _____ 4 Prefer not to say

3. Are you of Spanish/Hispanic/Latino origin? 1 No 2 Yes

4. What is your race? (Please check all that apply)

- 1 White
- 2 African-American or Black
- 3 American Indian/Alaska Native
- 4 Asian
- 5 Middle Eastern
- 6 Native Hawaiian/Other Pacific Islander
- 7 Other _____

5. What is your state of residence: _____

6. What are your current professional credentials? (Please check all that apply)

- 1 MD 2 OD 3 PharmD
- 4 BSN 5 MSN 6 PhD/DNP

7. What is your medical specialty: _____

8. How many years and months that you have worked in this specialty (including fellowship years):

Years / Months: _____ / _____

9. In an average week, how many hours per week do you spend treating / observing anesthetized or sedated pediatric patients?

Hours: _____

Version Date 03/21/2019

CONFIDENTIAL

**This document is confidential and the property of the Duke University.

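### Q14 and Q16 tell participants that the two scales are reverse scored just before the mapping: a leading cue on direction that PSSS levels 2–5 do not support

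*Combined protocol and SAP*

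**What the plan says.** Both versions of the interview guide (sections 22 and 23, each titled Appendix I) end with a mapping section. Q14 maps PSSS levels to the sedation definitions, Q15 maps UMSS levels to the same definitions, and Q16 maps the PSSS to the UMSS.

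- Q14, spoken before the mapping: "The PSSS is reverse scored as compared to the UMSS, so make sure you are referring to the correct scale".
- Q16, spoken before the mapping: "Remember that these are reverse scored compared to one another as we work through this activity".
- The Q16 form marks PSSS 5 and UMSS 0, at the top of their columns, both as Awake.

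The wording is the same in the PSSS-first and UMSS-first guides.

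The PSSS text (Appendix F) defines its upper levels by behaviour:

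- Level 2: "Patient is quiet (awake or asleep) and not moving, no frown, no verbalization, no crying".
- Level 3 concerns discomfort without movement, and adds: "May be awake or asleep".
- Level 4: "Patient is moving during the procedure and requires gentle immobilization or positioning". No state of arousal is given.
- Level 5 concerns movement that needs forceful restraint, and adds: "Patient may be sedated or awake".

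The UMSS (Appendix G) is graded by arousal, from awake and alert at 0 to unarousable at 4.

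**The concern.** The mapping section exists to learn how the categories on each scale line up with the definitions and with each other. That bears on the second co-primary endpoint (section 3.2), the clinicians' evaluation of how relevant the scale is for capturing sedation levels. Whether the PSSS orders depth of sedation at all is part of that question. Just before asking, the interviewer states as background that the two scales run in opposite directions.

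A participant who takes this at face value will tend to put the levels in reverse order. Some of the apparent agreement between the scales would then come from the prompt. The cases that break the order, such as a calm, fully awake child or a sedated child who is moving, become less likely to be mentioned in the mapping answers. Varying which scale comes first cannot offset this, because both order groups hear the same sentences.

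**Working it through.** The plan gives no figure on this point to reproduce. The check sets the level texts side by side and then counts how much the spoken sentence constrains the answer.

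**1. What each PSSS level is graded on (Appendix F)**

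| PSSS | Graded on | Arousal state in the text |
|---|---|---|
| 5 | Movement, forceful restraint | Sedated or awake |
| 4 | Movement, gentle restraint or positioning | Not given |
| 3 | Discomfort, no movement | Awake or asleep |
| 2 | Quiet, still | Awake or asleep |
| 1 | Airway support, normal physiology | Deeply asleep |
| 0 | Abnormal physiology | Deeply asleep |

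Three of the six levels (2, 3 and 5) expressly allow both states, and a fourth (level 4) is silent.

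**2. Where the opposite direction holds.** PSSS 0 and 1 are deep sleep. UMSS 3 is deep sleep and UMSS 4 is unarousable. At the deep end, low PSSS numbers go with high UMSS numbers. Even there, PSSS 0 and 1 differ by physiology and airway need, which the UMSS does not record.

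**3. Where it fails.** Take two children allowed by the texts:

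- Child A is still, quiet, awake and alert: PSSS 2, UMSS 0.
- Child B is sedated but moving so as to need forceful restraint: PSSS 5. Being sedated, the child is not awake and alert, so UMSS is at least 1.

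A reverse order requires the child with the higher PSSS to have the same or a lower UMSS. Here PSSS rises from 2 to 5 while UMSS rises from 0 to at least 1, so the order breaks.

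**4. How far the cue narrows the Q16 answer.** Inputs: six PSSS levels (0–5) and five UMSS levels (0–4).

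- An exact reversal, UMSS = 5 − PSSS, would send PSSS 0 to UMSS 5, which does not exist.
- All assignments of one UMSS level to each PSSS level: 5^6 = 15,625.
- Assignments in reverse order, ties allowed: C(10,6) = 210, and 210/15,625 = 1.3%.
- If PSSS 5 is also fixed at UMSS 0, as the form's labels suggest: C(9,5) = 126, and 126/15,625 = 0.8%.
- If every UMSS level must also be used: 5.

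**5. Q14.** Six PSSS levels to four definitions give 4^6 = 4,096 assignments. If a participant carries the ordering over to the definitions, which is an assumption, C(9,6) = 84 remain (84/4,096 = 2.1%).

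These counts show what the cue rules out and what it leaves open. They do not estimate bias, because the assignments are not equally plausible to a clinician.

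**The case against.** The strongest reply is that the sentence is a practical caution. In a telephone interview with two scales that both use the numbers 0 to 4, participants can easily read from the wrong sheet, and Q14 ties its remark to using the right one. That is fair for Q14. In Q16 no such clause follows, and the remark is to be kept in mind throughout the activity. Q15 shows that a reminder to check the sheet can be given without mentioning direction.

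A reader might infer that the guide declares the PSSS to be the UMSS turned round level for level, and so hands participants the answer. The documents do not support that. They state a direction and no pairings. Participants have just heard in Q12 that the PSSS has more categories, and 210 ordered mappings remain open (126 with the Awake anchor). Q14 asks about the definitions and not the UMSS, so the cue reaches it only indirectly.

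A reader might also argue from the row layout of the Q16 form, where reading across puts PSSS 2 beside UMSS 3. That does not stand either. Section 5 lists three documents for participants to use (the definitions and the two scales), and nothing says they see the interviewer's form or hear its labels.

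Finally, mapping is the last topic. Before it, in the PSSS-first numbering, Q5 probes movement, discomfort, sleep, physiology and airway, and Q6 asks about patients who fit more than one level. The UMSS-first guide asks the same in its Q7 and Q8. In both guides Q10 to Q12 cover ambiguity, alignment with the definitions and differences between the scales. Participants can therefore raise the mismatch before hearing the cue. This limits the harm to the study as a whole, but it does not take the cue out of the mapping answers.

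**Conclusion.** The point holds as a minor one. In every interview (18 to 24 planned), participants hear twice that the scales run in opposite directions, immediately before two of the three mapping tasks. The scale texts bear this out at the deep end and not across PSSS 2–5. The likely effect is that mapping answers look more concordant than the wording of the scales warrants, mainly in Q16. Its size cannot be worked out from the documents: section 6.2 plans qualitative coding and an item-tracking matrix, with no agreement statistic between scales. The conclusion assumes that interviewers read the sentences as printed and that participants take them as a statement about order.

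Separately, the Awake label on PSSS 5 in the Q16 form conflicts with Appendix F, which lets a level 5 patient be sedated. That inconsistency stands whether or not participants ever see the form.

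**What to change.** In Q14 and Q16 of both guides, replace the reverse-scoring sentence with a neutral reminder, for example: *The same number does not mean the same thing on the two scales; please check which scale you are looking at and go by the description of each level, not its number.* This keeps the protection against mixing up the sheets and drops the stated direction.

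In the Q16 form of both guides, remove the Awake labels, or reconcile the one on PSSS 5 with Appendix F.

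The cost is four replaced sentences (two in each guide) and one form edit in each guide. It adds no interviews, interview time or analysis. Because the guides are appendices to the protocol, the change would go to the EC/IRB as an amendment under section 9.
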